There is a significant revolving door of incarceration among homeless adults, a population with substantial health disparities. Homeless adults who receive the professional coordination of individualized care (i.e., case management) during the period following their release from jail experience fewer mental health and substance use problems, are more likely to obtain stable housing, and are less likely to be re-incarcerated. The proposed study will use mobile technology to address these barriers and fill gaps in the understanding of the causes of the revolving door of homeless incarceration. Specifically, 462 homeless adults who enroll in a shelter based Homeless Recovery Program after release from county jail will be randomly assigned to one of three treatment groups: 1) usual shelter-based case management (UCM), 2) UCM plus a study provided smartphone (UCM+SP), and 3) UCM with a study provided smartphone that is preloaded with an innovative care management app (SPCM). The SPCM app is an extension of the research team's previous successful work using mobile devices to assess and modify health behaviors in low income and homeless adults. Those assigned to SPCM will receive smartphones that will prompt (twice weekly) connections to shelter based case managers. The app will also offer direct links to care managers (available during normal business hours) and crisis interventionists (available 24 hours a day, 7 days a week), with the touch of a button. It is hypothesized that SPCM will increase utilization of case and crisis management services thereby addressing unmet needs (e.g., obtaining shelter, clothing, counseling, identification) and reducing homelessness and re-arrest. Another key focus of this study is to address gaps in the understanding of mechanisms that drive re-arrest and homelessness by using traditional in-person (i.e., baseline, 1, 3, and 6 months post-baseline) and smartphone based (i.e., daily for 6 months) assessment methods to identify distal and proximal predictors (e.g., affect, thoughts, behaviors, events) of continued homelessness and arrest. This research represents a step toward integrated service connection and healthcare service provision for one of the most undeserved, high need, and understudied populations in the United States. Smartphone apps that increase the use of available healthcare services and identify predictors of key outcomes (e.g., homelessness, re-arrest, medication compliance) could be used to reach hard to reach populations with histories of significant and persistent health disparities (e.g., homeless adults).

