- c. **To identify key factors (alcohol and drug use, social support, psychological distress, quality of life) that predict re-arrest and nights spent homeless using traditional and smart phone-based assessment approaches.** It is hypothesized that key variables that are measured in- person (e.g., alcohol/drug use, perceived social support, psychological distress, quality of life) and via daily phone-based assessments (e.g., affect, stress, discrimination, alcohol/drug use) will have direct effects on re-arrest and number of homeless nights. These key variables are also hypothesized to mediate the relation between treatment condition and number of homeless nights and re-arrest.

Study Design:

This study is a 3-arm randomized controlled trial. Specifically, male and female homeless adults who enroll in a shelter based homeless recovery program following release from either the Dallas County Jail or the Dallas City Jail (N=462) will be randomized to one of three conditions: Usual Case Management (UCM); Usual Care plus Smartphone (UCM+SP); or Usual Care plus Smartphone based Case Management (SPCM). SPCM will be delivered through a modified version of the PI's previously developed smartphone application (i.e., "app") on a study provided smartphone. The app will not provide case management and crisis intervention services directly; rather, it will prompt twice weekly contact with their case manager and provide links to service providers through the touch of a button. Primary study outcomes are service utilization, number of homeless nights, and re-arrest. Another key focus of this study is to address gaps in our understanding of the factors that drive re-arrest and homelessness by using traditional in-person (i.e., baseline, 1, 3, and 6 months post- baseline) and smartphone based (i.e., daily for 6 months) assessment methods to identify distal and proximal predictors of continued homelessness and arrest. Arrest records will be examined to determine if participants are re-arrested within 12 months of study enrollment.

Participants who are randomly assigned to the UCM+SP or SPCM conditions will receive a smartphone at the randomization visit and they will be asked to carry it with them at all times for 6 months (26 weeks). Date, time, location, and duration of SPCM app feature use (e.g., case manager calls) will be recorded by the app for future analysis. See Table 1 for a summary of study conditions.

Study Conditions

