All randomized participants will be included in the analyses and the trial will end once 462 participants are randomized and complete all study components. Preliminary data analyses, manuscript preparation, and conference presentations will begin in Year 2.

Aim 1. The number of participants ($n = 144$ in each group) was estimated based on the following assumptions: 1) random allocation of participants between 3 conditions; 2) type I error rate set to 0.05; 3) a 30% dropout rate for each condition;²³ 4) targeted minimum power of 0.9, and 5) a conservative increase of 4.5 case management sessions between the UCM and SPCM conditions across the 6-month study period. The estimated increase in in case management sessions is based on Lucht et al.,⁴⁹ which showed that 20% of all phone-based prompts to connect with an alcohol treatment counselor resulted in actual treatment sessions. Mondays, the daily EMA items and additional items will be assessed. Additional Monday items will cover topics/variables that have less day-to-day variability (e.g., arrest; witnessing crimes or violence; emergency room visits; hospitalization; quality of life). Examples of EMA constructs that will be assessed are listed in Table 3 and actual EMA items are included in the Appendix.

	Compensation (Usual Care)	Compensation (Smartphone Groups)
Visit 1 (Today)		
Questionnaire	\$30	\$30
Visit 2 (Within 3 Days)	\$30	\$30
Visit 3 (1-Month Follow-Up)		
Questionnaire	\$50	\$50
Phone Assessments	N/A	Up to \$50 every 15 days for survey completion (\$100)
Visit 4 (3-Month Follow-Up)		
Questionnaire	\$50	\$50
Phone Assessments	N/A	Up to \$50 every 15 days for survey completion (\$200).
Visit 5 (6-Month Follow-Up)		
Questionnaire	\$50	\$50
Phone Assessments	N/A	Up to \$50 every 15 days for survey completion (\$300).
TOTAL:	Up to \$210	Up to \$810

Analyses. Primary analyses for this aim will compare counts of the total number of case and crisis management sessions that occurred between the randomization visit and the 6-month follow-up across the 3 conditions using analysis of covariance (ANCOVA). Covariates may include race/ethnicity, age, sex, lifetime months homeless, type of arrest (e.g., violent vs. non-violent), substance abuse or mental health diagnoses,

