and education. The Tukey-Kramer adjustment will be used to examine all pairwise comparisons across conditions. We will also determine if the intervention has similar effects across races, gender, and age**Aim 2**. Based on the available data in criminal justice and homeless populations, we expect a 30% reduction in alcohol and drug use days in SPCM and a 15% reduction in alcohol and drug use days in UCM+SP compared with UCM.^{3,126} Given these expected differences, the proposed sample size of 462 participants (144 per condition) will yield 90% minimum power for comparing the frequency of alcohol and drug use days across conditions. Furthermore, the proposed sample size of 462 participants has 80% minimum power to detect a 24% greater decrease in psychiatric symptoms¹²⁷ in the SPCM group and 10% greater decrease in the UCM+SP group relative to UCM.

Analyses. Multi-level models, also known as mixed models will assess the impact of condition on alcohol and drug use and psychological distress. This method considers the auto correlated nature of this data, and 'unstructured' covariance may be specified to account for the unequal spacing of observations (in-person and EMA data). Covariates for analyses will include baseline characteristics that are known predictors of each outcome, including age, race/ethnicity, employment status, criminal history, and periods of lifetime homelessness. We will also test for interactions between treatment and key demographic variables (e.g., race, ethnicity, gender, and age).

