Aim 3. The detectable effects for analyses based on a complete EMA sample size of 201 participants (allowing for 30% study drop-out; see [name] and Rosenheck³ for follow-up rates in a sample of homeless adults with both serious mental illness and substance abuse), 2-sided tests, alpha=.05, and power=.80 are presented in Table 8. Where appropriate, these estimates account for the fact that repeated observations from the same person will be correlated. The most conservative detectable effects for the GLMM EMA analyses will be presented. Thus, calculations are based on an N of 201 individuals completing 80% of 183 assessments during the 6-month EMA study period for a total of 29,426 EMAs across all participants. Since few EMA studies have been conducted in this population, we computed detectable effects using a reasonable range of intraclass correlation coefficient (ICC) values. Detectable effects estimates depend on the variance inflation factor (VIF)¹³⁴ which is based on both the size of the ICC and the average number of observations per person. The VIFs used to calculate the effective sample size are displayed in Table 8. Thus, using the EMA data, we will be able to detect factors that predict reductions in homeless nights by as little as 3.1 percentage points.

Analyses. Logistic Regression of traditional in-person assessments (e.g., substance use, social support, psychological functioning, quality of life; see Table 7 for other key constructs) and summarized EMA data (e.g., affect, stress, discrimination, alcohol and drug use) will be conducted to identify significant demographic, psychosocial, environmental, and behavioral predictors of re-arrest in the 12 months following the randomization visit (binary outcome). Covariates may include treatment group, age, gender, race/ethnicity, education, type of crime, and other variables as appropriate. Change scores (e.g., change in social support from baseline to the 1-month follow-up visit) will also be examined as potential predictors of re-arrest.

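### The total of 462 and the 144 per condition do not agree (3 x 144 = 432), and the N behind the two Aim 2 power figures cannot be determined

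*Combined protocol and SAP*

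**What the plan says.** The total is 462 wherever it appears, and three places apply it to those randomized:

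- General Information: "462 homeless adults who enroll in a shelter based Homeless Recovery Program after release from county jail will be randomly assigned".
- Study Design: "N=462) will be randomized to one of three conditions".
- Statistics, opening paragraph: "the trial will end once 462 participants are randomized".

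The Population entry and the Study Population section also give 462, as the number recruited or included.

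The per-condition figure is different. Aim 1 opens with "The number of participants ($n = 144$ in each group) was estimated based on the following assumptions". Aim 2 puts both numbers in one phrase, "the proposed sample size of 462 participants (144 per condition) will yield 90% minimum power", and then makes a second power statement with the total alone: "the proposed sample size of 462 participants has 80% minimum power".

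Aim 3 starts from "a complete EMA sample size of 201 participants (allowing for 30% study drop-out" and bases its detectable effects on "an N of 201 individuals completing 80% of 183 assessments during the 6-month EMA study period for a total of 29,426 EMAs". Only the two smartphone conditions supply these daily assessments, and the Visit 2 description gives phones to two-thirds of participants.

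**The concern.** The Aim 2 phrase presents 144 as the breakdown of 462 over three conditions, and it is not. This is more than a stray digit: 144 appears in both Aim 1 and Aim 2, and the Aim 3 base depends on it. The calculations in Aims 1 and 3 fit a trial of 432, while the design and the recruitment target describe a trial of 462.

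At stake is whether the power claims can be read. The Aim 2 text gives no standard deviation or baseline rate, so a reader cannot recompute the 90% or the 80% to find out which N produced them. Only the sponsor can say.

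**Working it through.** **Inputs from the plan.** Total 462 (General Information, Study Design, Statistics). Three conditions, two with phones (Study Design). 144 per condition (Aims 1 and 2). Dropout 30% (Aims 1 and 3). 80% completion of 183 assessments (Aim 3). Detectable effect 3.1 percentage points (Aim 3). Equal allocation is inferred from the single group size and the two-thirds with phones.

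**1. Total against per-condition size.**
- 3 x 144 = 432
- 462 / 3 = 154
- 462 - 432 = 30, and 30 / 462 = 6.5%

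**2. Reproducing Aim 3.** Base = 2 x n x (1 - 0.30); assessments = base x 0.80 x 183.

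| n per condition | Phone recipients | Base | Assessments |
|---|---|---|---|
| 144 | 288 | 201.6, cut to 201 | 201 x 0.80 x 183 = 29,426.4 |
| 154 | 308 | 215.6, cut to 215 | 215 x 0.80 x 183 = 31,476 |

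The first row matches both printed figures (201 and 29,426). The second matches neither. Working back, 201 / 0.70 = 287 phone recipients, and 287 x 1.5 = 431 in total.

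**3. Can the 30 be explained?**
- *Unequal allocation.* Two phone conditions of 144 would leave 462 - 288 = 174 in usual care. But Aim 1 gives 144 for each group, Aim 2 gives it per condition, and 288 / 462 = 62.3% is not two-thirds.
- *Dropout.* Aim 1 lists the 30% among the assumptions that led to 144, so it is already inside that number. If 144 were completers instead, enrolment would be 144 / 0.70 = 205.7 per condition, or 617 in total. A fall from 154 to 144 is a 6.5% loss that the plan does not mention. To get 201 from 308 phone recipients needs 1 - 201/308 = 34.7% dropout.
- *Loss between Visits 1 and 2.* Study Procedures removes people not randomized within 14 days, but General Information and Study Design apply 462 to those randomized.

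**4. Size of the effect if the figures were calculated at 144 per condition and 154 are enrolled.** This is illustrative: a two-sided comparison of two equal arms at alpha 0.05, with the stated power taken as exact. New power = Φ[(1.960 + z) x √(154/144) - 1.960], where √(154/144) = 1.0341.
- 90%: (1.960 + 1.282) x 1.0341 - 1.960 = 1.392, which is 91.8%.
- 80%: (1.960 + 0.842) x 1.0341 - 1.960 = 0.937, which is 82.6%.

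Applying 30% dropout to both sizes leaves the ratio unchanged.

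For Aim 3, with the same intraclass correlation and the same number of assessments per person, the effective sample size is proportional to the number of participants. So 3.1 x √(201/215) = 3.00 percentage points.

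**The case against.** The strongest reply is that the inconsistency probably does no harm. Every statement of the total says 462, and every figure whose base can be traced rests on 144. On that reading the sponsor enrols more than the calculation requires, and the stated powers, which are called minimums, are still met. This largely stands and limits the size of the point. It does not remove it: the plan never says that 462 includes a margin, and the Aim 2 phrase presents 144 as the breakdown of 462.

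A reader might infer that no figure in the Statistics section can be tied to an N. The documents do not support that. Aim 3 states its N as 201, and Aim 1 ties its calculation to 144 in each group. The doubt about which N was used is confined to the two Aim 2 power statements.

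A reader might also infer that the trial falls short of its stated power. That would need the power to have been calculated at 462 and only 432 to be enrolled. No section sets 432 as a target, so this describes a trial that nobody plans.

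Two caveats on the evidence also stand. The Statistics sentence on when the trial ends goes on to require completion of all study components, which sits awkwardly with 30% dropout; General Information and Study Design are the firmer support for 462 randomized. And the power conversions are illustrative: Aim 2 states neither alpha nor sidedness, and its planned analysis is a mixed model rather than a two-arm test.

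**Conclusion.** The sample size is wrong as written. A total of 462 and 144 in each of three equal conditions cannot both hold, and neither allocation, dropout nor loss before randomization accounts for the 30. Aims 1 and 3 rest on 432. For Aim 2, the 90% is attached to both numbers and the 80% to 462 alone, so their N cannot be determined from the documents.

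The practical effect is modest. If everything was calculated at 144 per condition, the plan is slightly conservative at 462: gains of about 1.8 and 2.6 points of power, and 0.1 percentage point in the Aim 3 detectable effect. These sizes assume that the stated power is exact, a two-sided alpha of 0.05, equal arms, and an unchanged intraclass correlation. The arithmetic contradiction needs none of these assumptions. It should be corrected because it concerns the sample size on which the plan relies.

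**What to change.** Reconcile the total and the per-condition number across Aims 1 to 3 of the Statistics section, in one of two ways:

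- **(a)** State 462 as 154 per condition, replace the Aim 3 base with 215 participants and 31,476 assessments, and recompute the Aim 3 detectable effects.
- **(b)** State that 144 per condition (432 in total) is the calculated requirement on which the Aim 1 and Aim 3 figures rest, and give the reason for enrolling 462. The 201 and 29,426 can then stay, labelled as resting on 432.

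Under either option, state which N each Aim 2 power figure used, and restate the power if needed.

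Option (b) may need only a sentence or two; option (a) needs a short recalculation. Neither adds participants or changes the design, since 462 remains the total in both. The only cost is that some stated powers or detectable effects may shift by the small amounts shown above.

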Our own research in the summer of 2013 indicated that cell phone ownership is common among homeless adults, with 58.4% reporting that they had active cell phone service (there are government programs that pay for cell phone service for very low-income adults). Other studies have indicated that 70% of homeless adults who have cell phones use them to connect with peers and family members, 32% carry a phone for safety reasons (e.g., access to emergency services), and 23% use a phone to communicate with current or potential

employers.³⁵⁻³⁷ Another study demonstrated that although 62% of homeless youths possessed activated cell phones, only 17% were using their cell phone to connect to case managers.³⁶ Thus, initial evidence indicates that cell phones are already being used in homeless populations, but few homeless adults are using their phones to contact case managers who have the primary role of linking individuals to care and coordinating care for those in need. **Thus, a significant opportunity for novel interventions is being missed.**

Smartphone apps may be a novel way to offer direct access to case management, and may be a practical and useful means by which to reduce barriers to service utilization in vulnerable and hard to reach populations. It is notable that smartphone service plans are no longer cost prohibitive to conducting intervention research. For instance, in our previous studies that have used smartphones, the cost for an activated smartphone with monthly talk, text, and internet has been under \$30 per month (the cost for the phone is included in the monthly fee), which is equivalent to less than the cost of 1/2 of 1 day in the Dallas County Jail.

Aside from demographic variables and history of mental illness and/or substance use/abuse, very few predictors of re-arrest and sustained homelessness have been identified.⁴ To date, all studies that have examined predictors of incarceration, re-arrest, health, and continued homelessness among homeless adults have used traditional in-person assessment methods that are usually conducted retrospectively or months/years before the predicted outcome.^{4,11,33,38-41} **Studies have indicated that traditional assessment methodologies provide biased and/or inaccurate estimates due to recall bias and errors in memory**

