(e.g., assessing the number of drinks consumed or level of depression or anxiety over the past week or month).^{42,43} Ecological momentary assessment (EMA), in which handheld devices are used to capture “real time” experiences that vary daily (or from moment to moment), is currently the most accurate way to measure phenomena in real time in natural settings.^{42,44} Although EMA has been used in a variety of populations and with multiple health outcomes, only one study⁴⁵ outside of our own work⁴⁶ has collected EMA data in homeless adults. The proposed study will identify key variables, measured proximally (EMA data) and distally (traditional in-person assessments and EMAs), that predict re-arrest and homelessness. These rich data will address knowledge gaps that have limited our understanding of and ability to intervene in this marginalized population.

Overall, the significance of this trial will be to evaluate a technology-driven application to increase access to service providers in a highly vulnerable group of homeless adults and to thereby decrease the likelihood of re-arrest and homelessness. In addition, we hope to improve our understanding of the proximal and distal factors that contribute to homelessness and incarceration recidivism. This contribution is significant because it is a step towards the development of practical, inexpensive, and effective interventions for homeless adults.

Objectives:

Our long-term goal is to reduce health disparities among recently incarcerated homeless adults.

The primary study objectives will be attained by pursuing the following specific aims:

- a. **To compare case management and crisis management service utilization among recently incarcerated homeless adults who are randomized to the UCM, UCM+SP, and SPCM conditions.** It is hypothesized that homeless adults assigned to SPCM will utilize more case management and crisis management services than those assigned to UCM or UCM+SP.
- b. **To compare the effect of treatment condition on alcohol use, drug use, and psychological distress.** It is hypothesized that the SPCM group will demonstrate greater improvements in each outcome compared to UCM+SP or UCM

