2. **EMA data.** Individuals randomized into the 2 smartphone conditions (i.e., UCM+SP and SPCM) will receive a smartphone at the randomization visit and will be asked to carry the phone with them at all times for 6 months (26 weeks). All participants randomized to a smartphone condition will be trained to use the smartphone app for data collection and resource utilization purposes, and participants will be instructed to call study staff in the event that they are having difficulty with the phone. These participants will be asked to complete one EMA each day, administered through a secure smartphone application (i.e., app). Smartphones will be programmed to automatically cue an assessment each day 30 minutes after the participant’s self-reported usual waking time. The “usual waking time” is reported by the participant to the research staff at the randomization visit, and may vary by day of the week. If the participant does not acknowledge the EMA, it will be rescheduled for later that day to increase the likelihood that EMAs are completed. Participants will respond to EMA questions on the smartphone using the touch screen. Daily EMAs will inquire about the substance use, sleeping arrangements, stress, discrimination episodes, etc., from the previous day. In addition, EMAs will ask participants to rate their emotional state (e.g., affect, stress level,). The smartphone app will also collect geolocation data up to every five minutes of the study, regardless of app use.

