Participants have reported few problems using the QDS program, including those with no computer experience. Staff will be available to help participants who may have difficulty. The amount of time needed to complete the QDS administered questionnaires varies by study visit. Based on our previous experience with collecting data in homeless adults we estimate that the baseline visit will require approximately 1-2 hours to complete and follow-up assessment visits will require approximately 1-2 hours. Note that although breaks have been encouraged in our previous studies that have used QDS assessments in this homeless population, none actually took breaks. Examples of traditional measures are listed in Table 2 and include multiple constructs that are hypothesized to directly and indirectly (i.e., mediation of the treatment effect) affect the study outcomes. In addition, barriers to phone-based case management sessions and staff and participant perceptions of the SPCM app will be assessed.

See Appendix A for measure descriptions, assessment items, and a schedule that indicates which measures will be administered at each visit. In addition to the QDS System, assessment data may be collected through the REDCap system. REDCap is a secure web application for building and managing online surveys and databases and is specifically tailored for the management and administration of online data collection for research studies.

Alcohol/drug use, re-arrest, and number of homeless nights will be collected using a Timeline Follow-back procedure (See Appendix) at all 1, 3, and 6-month follow-up visits. In addition, arrest data from the Dallas County Jail and the Dallas City Jail will be examined to identify participants who are re-arrested within 12- months of the randomization visit (see **Director of Criminal Justice Letter of Support**). This will provide an objective measure of the date and time of arrest as well as a description of the offenses that occurred. The research team will share participant's name and date of birth to obtain this information, but no additional information that the participant provides to us over the course of the study will be shared with this Dallas County employee or the Jail. For participants who complete online surveys via REDCap, the participant will be instructed to call the research team to complete the Time Line Follow Back for location, drug and alcohol use.

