Generalized Linear Mixed Model Regression Analyses (GLMM) will be used to examine the longitudinal effect of key risk and protective factors on number of homeless nights (measured repeatedly using a timeline follow-back procedure at in-person follow-up visits). GLMM can handle fixed and random effect model parameters, nested designs, and repeated measures with various correlation structures.^{128,129} GLMM can also handle different variance functions, unbalanced designs where the number of repeated observations varies across individuals, and the situation where assessments within a week are more highly correlated than assessments separated by multiple weeks or months. We will assess the best way to model the correlation of the repeated measures using the methods of Wolfinger¹³⁰ and statistics such as Akaike's and Schwarz's information criteria. Adjustments for multiple comparisons will be made according to Westfall and Young.¹³¹

GLMM will also be used to identify proximal predictors of homeless nights (assessed each day) using EMA data. EMAs generate an enormous amount of data; therefore, we will be able to address multiple within

and between subject questions. For example, we will examine key EMA variables (e.g., negative affect, stress) and parameters (e.g., intercept, slope, quadratic term, volatility) as potential predictors of homeless nights. This invaluable information may be used to detect high-risk situations that may be targeted in future “smart interventions.” EMA data will also allow us to address other important exploratory questions like: 1) what psychosocial changes occur as an individual moves from homelessness into housing, and 2) what effect do events like exposure to discrimination, violence, or hospitalization have on homeless nights.

Mediation. The PROCESS macro for SPSS/SAS (described in Hayes, 2013;¹³² and available online¹³³) will be used to conduct exploratory mediation analyses to identify variables that mediate the relation between condition and homeless nights and re-arrest outcomes. This method uses an ordinary least squares path analytic framework to estimate direct and indirect effects in single and multiple mediation models with bootstrapped confidence intervals. The macro can also be used to evaluate moderated mediation models including those with dichotomous outcomes (e.g., arrest vs. no arrest).

Ethics:

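### Could the Aim 2 three-arm comparisons be distorted because daily phone data exist in only two of the arms?

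*Combined protocol and SAP*

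**What the plan says.** In the Statistics section, Aim 2 expects alcohol and drug use days to fall by 30% in SPCM and 15% in UCM+SP relative to UCM, and states that the sample "will yield 90% minimum power for comparing the frequency of alcohol and drug use days across conditions". The analysis is a mixed model for the effect of condition on substance use and distress. Its one reference to source is that an unstructured "covariance may be specified to account for the unequal spacing of observations (in-person and EMA data").

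EMA is a two-arm source. Under Sources of Materials, "Individuals randomized into the 2 smartphone conditions (i.e., UCM+SP and SPCM) will receive a smartphone at the randomization visit", and only those participants are asked for the daily survey. The compensation table shows no phone assessments for usual care.

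A source common to all arms is also scheduled. Under Traditional Measures, "Alcohol/drug use, re-arrest, and number of homeless nights will be collected using a Timeline Follow-back procedure" at the 1-, 3- and 6-month visits. Table 2 lists the questionnaires on mental health and affect.

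Aim 3 is more explicit. Homeless nights are "measured repeatedly using a timeline follow-back procedure at in-person follow-up visits" in one model, and for the other, "GLMM will also be used to identify proximal predictors of homeless nights (assessed each day) using EMA data".

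**The concern.** Read alone, the Aim 2 analysis text seems to put both sources into one three-arm model. UCM would then contribute visit recall only, while the phone arms would contribute mostly EMA, so measurement method would be partly confounded with arm. The Background says that "traditional assessment methodologies provide biased and/or inaccurate estimates due to recall bias and errors in memory", and gives as examples "assessing the number of drinks consumed or level of depression or anxiety over the past week or month". Those are constructs of the Aim 2 kind, so by the plan's own account the two sources need not agree in level.

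If they were pooled without a term for method, a level difference would add to or offset the expected 15% and 30% reductions against UCM. SPCM versus UCM+SP would be untouched as long as the difference is the same in both phone arms. A choice of source made after seeing the data would also leave room for selection.

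**Working it through.** **1. The plan's own figures.** EMA base: 2 arms × 144 × (1 − 0.30) = 201.6, stated as 201. Then 201 × 0.80 × 183 = 29,426.4, stated as 29,426. Both reproduce and confirm that EMA covers two arms.

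The 90% power for use days cannot be reproduced, because no mean or SD is given. With 144 per arm and two-sided alpha 0.05 (assumed for Aim 2), a 30% reduction needs a coefficient of variation of at most 0.30 / [(1.960 + 1.282) × √(2/144)] = 0.785. This does not tell us which source was meant.

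**2. Which source the plan gives each outcome.**

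| Place | Alcohol and drug use | Psychological distress | Role of EMA |
|---|---|---|---|
| Objectives, aim c | listed in person and by phone | listed in person only | affect, stress, discrimination, substance use |
| Sources of Materials, item 1 | timeline follow-back with study staff | self-report questionnaires, all participants | – |
| Traditional Measures; Table 2 | timeline follow-back at 1, 3 and 6 months | several scales, including the Patient Health Questionnaire | – |
| EMA Measures | – | – | finding predictors, with a pointer to Aim 3 |
| Statistics, Aim 2 power | use days, the quantity timeline follow-back yields | psychiatric symptoms | – |

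Only alcohol and drug use has two candidate sources, and the other entries for it point to timeline follow-back.

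**3. The covariance remark.** It is permissive. An unstructured matrix for T occasions has T(T + 1)/2 parameters: 6 for 3 visits, 10 for 4, and 16,836 for 183 EMA days against about 201 EMA completers. Visits at 1, 3 and 6 months are unequally spaced, so the structure suits visit data. It cannot be fitted to the daily series.

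**4. What pooling would do.** The assumptions are not in the plan: a method difference d of 0.1 or 0.2 SD, no true effect, total SD 1, a random intercept with ICC 0.3, 0.5 or 0.7, 144 × 0.7 ≈ 101 completers per arm, and no time or method term. With m rows per person, the variance of a person's mean is ICC + (1 − ICC)/m. The bias in a UCM contrast is w × d, where w is the EMA share of phone-arm rows. EMA rows per person: 0.80 × 183 ≈ 146. The false-positive rate is P(|Z + bias/SE| > 1.96).

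Example, ICC 0.3 with 3 visit rows: SE = √{[(0.3 + 0.7/3) + (0.3 + 0.7/149)]/101} = 0.0911.

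| Data in the model | w | SE at ICC 0.3 / 0.5 / 0.7 | False positives, d = 0.1 | False positives, d = 0.2 |
|---|---|---|---|---|
| 3 visit rows + EMA, equal residual variance | 146/149 = 0.980 | 0.0911 / 0.1076 / 0.1219 | 18.9 / 14.9 / 12.7% | 57.6 / 44.5 / 36.2% |
| Follow-back by day (183 rows, assumed) + EMA | 146/329 = 0.444 | 0.0775 / 0.0997 / 0.1178 | 8.8 / 7.3 / 6.6% | 20.9 / 14.5 / 11.7% |
| 3 visit rows only | 0 | 0.1028 / 0.1149 / 0.1259 | 5% | 5% |

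The first line treats a visit row that summarizes one to three months as no more precise than a single day. If the three rows are instead weighted by assumed intervals of 30, 60 and 90 days (independent days), w = 146/(146 + 180) = 0.448. The rates at d = 0.2 then fall to 21%, 15% and 12%, as in the second line. A pooled model with a separate mean for every EMA and visit occasion has zero bias and a 5% rate.

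On the use-day scale, let EMA capture r times what recall captures. The apparent reduction is 1 − (1 − true) × [1 + w(r − 1)]. With w = 0.444 and r = 1.1 or 0.9, a true 30% appears as 27% or 33%, and a true 15% as 11% or 19%. With w = 0.980 the figures are 23% or 37%, and 7% or 23%, under the same equal-variance condition.

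**5. What pooling would gain.** Using visits only raises the SE by 0.1028/0.0911 − 1 = 13% at ICC 0.3 and 0.1259/0.1219 − 1 = 3% at ICC 0.7. With follow-back by day the loss is under 0.2%. There is little reason to pool.

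**The case for a change.** The best case for acting is that the parenthesis is the only mention of source in the Aim 2 analysis text, while Aim 3 names a source for each of its homeless-nights models. The Background warns that the sources differ, substance use is collected both ways, and one sentence would settle the matter at no cost in data.

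Some of this stands. The allocation of sources to contrasts is not written out, and no single distress scale is named for Aim 2. The second gap does not create the confounding described, because the candidate distress scales are visit questionnaires given to all participants. Visit mode can also vary (in person, by phone, online), but that is open to every arm.

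The rest is weaker. The plan nowhere proposes a pooled model without a method term. The Background examples concern ordinary recall over a week or month; they do not address calendar-based follow-back and give neither size nor direction. The high error rates need an assumed difference, naive pooling, and equal weight for rows of different kinds, all at once.

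**Conclusion.** No change to the plan is needed. The Aim 2 text leaves out a detail that the rest of the protocol largely supplies: timeline follow-back use days and visit-based distress scales for the three-arm contrasts, with EMA directed mainly at Aim 3. A competent analyst following the plan would reach sound contrasts with UCM, and pooling would offer a precision gain of only 3–13% in SE at most.

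The inflation figures (12–21%, or 36–58% under equal row variance) are illustrations. They rest on an assumed 0.2 SD method difference, an assumed ICC range, and a model the plan does not specify; they are not estimates of an error in this trial. The stakes are also limited, since the Study Design section names service utilization, homeless nights and re-arrest as the primary outcomes, and the Aim 2 outcomes are not among them. Confidence is moderate: the reading rests on several sections taken together, because no single sentence states the allocation.
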